12.10 Appendix 10. Patient Health Questionnaire 9 (PHQ-9)

Over the last 2 weeks , how often have you been bothered by any of the following problems? (Use ** to indicate your answer)	Not at all	Several days	More than half the days	Nearly every day
1. Little interest or pleasure in doing things	0	1	2	3
2. Feeling down, depressed, or hopeless	0	1	2	3
3. Trouble failing or staying asleep, or sleeping too much	0	1	2	3
4. Feeling tired or having little energy	0	1	2	3
5. Poor appetite or overeating	0	1	2	3
 Feeling bad about yourself — or that you are a failure or have let yourself or your family down 	0	1	2	3
 Trouble concentrating on things, such as reading the newspaper or watching television 	0	1	2	3
 Moving or speaking so slowly that other people could have noticed? Or the opposite — being so fidgety or restless that you have been moving around a lot more than usual 	0	1	2	3
Thoughts that you would be better off dead or of hurting yourself in some way	0	1	2	3
For office cools	ig 0 +		Total Score	

Approved

If you checked off any problems, how difficult have these problems made it for you to do your work, take care of things at home, or get along with other people?

Not difficult at all	Somewhat	Very	Extremely difficult

Amendment 3

Protocol Title: A Phase 1b, Randomized, Double-blind, Placebo-controlled, Multiple Ascending Dose Study to Evaluate the Safety, Tolerability, Pharmacokinetics and Pharmacodynamics of AMG 598 in Subjects With Obesity

Amgen Protocol Number: AMG 598 20170139

Amendment Date: 25 June 2019

Rationale:

The following updates were made to the protocol, dated 15 February 2019:

- The dose regimen for Cohort 7 was added following the review of available safety and PK data from cohorts 1 through 6
- Inclusion and exclusion criteria were modified for cohort 7 to allow chronic stable medical conditions, including updates to laboratory reference ranges, and allowed concomitant medications
- A Safety Surveillance Team (SST) was added for ongoing safety review of Cohort 7 emergent data
- Criteria for rechallenge of Amgen investigational product after potential hepatotoxicity were added
- Visit windows were added to the cohort 7 Schedule of Assessments
- Bone mineral density (BMD) measurement clarified to state specifically in spine and hip/femur in cohort 1-6 DXA description
- Mental health questionnaire appendices updated to include the specific forms to be used at the sites

Amendment 2

Protocol Title: A Phase 1b, Randomized, Double-blind, Placebo-controlled, Multiple Ascending Dose Study to Evaluate the Safety, Tolerability, Pharmacokinetics and Pharmacodynamics of AMG 598 in Subjects With Obesity

Amgen Protocol Number: AMG 598 20170139

Amendment Date: 15 Feb 2019

Rationale:

The following updates were made to the protocol, dated 07 November 2018:

- Cohort 7 visits and procedures were streamlined to reduce complexity and burden on subjects completing the study.
- Primary analysis of data from escalation cohorts 1-6 was added in additional to final analysis of all subjects in cohorts 1-7.
- Objective and endpoint language was updated to clarify that potential biomarkers, including but not limited to inflammatory and adipose tissue markers, are one of the PD effects of AMG 598 that will be evaluated in this study.
- Protocol language was updated to reflect that spine and femur bone mineral density will be evaluated by dual energy x-ray absorptiometry (DXA) in subjects in cohorts 1-6, while total body composition, including bone mineral content, will be evaluated by DXA in subjects in cohort 7.
- DXA visit windows added.
- Typographical and formatting errors throughout the protocol were fixed.

Amendment 1

Protocol Title: A Phase 1b, Randomized, Double-blind, Placebo-controlled, Multiple Ascending Dose Study to Evaluate the Safety, Tolerability, Pharmacokinetics and Pharmacodynamics of AMG 598 in Subjects With Obesity

Amgen Protocol Number: AMG 598 20170139

Amendment Date: (

07 November 2018

Rationale:

In response to an FDA request, analysis of AMG 598 anti-drug antibody (ADA) samples will be conducted. In addition, the exclusion criteria were updated to exclude previous exposure to AMG 598.

Typographical errors and inconsistencies throughout the protocol were fixed.

			9.7.2.4	Weight, Waist Circumference and BMI:	21
10.	Chang	ges From	Protocol-sp	ecified Analyses	21
11.	Literat	ture Citati	ons / Refer	ences	22
12.	Priorit	ization of	Analyses		25
13.	Data I	Not Cover	ed by This	Plan	25
14.	Apper	ndices			26
	Apper		• •	lissing or Incomplete Dates for Adverse nitant Medications	27
		14.1.1		n Rules for Partial or Missing Stop Dates:	
		14.1.2		n Rules for Partial or Missing Stop Dates	
	Anner			alues/Clinical Severity grading	
	Apper	IUIND. N		aues/onnical Sevency grading	

Abbreviation or Term	Definition/Explanation
AE	adverse event(s)
AUC	area under the concentration-time curve
BMI	body mass index
СІ	confidence interval
C _{max}	maximum serum concentration
DLRM	Dose level review meeting
DXA	Dual-energy x ray absorptiometry
CTCAE	Common Terminology Criteria for Adverse Events
ECG	12-lead electrocardiogram
eCRF	electronic case report form
EOS	End of Study
FFA	Free fatty acid
GIP	Glucose-dependent insulinotropic polypeptide
GLP-1	Glucagone-like peptide-1
HbA1c	Hemoglobin A1c
HDL-C	High density lipoprotein cholesterol
HR	heart rate
IP	investigational product
IPD	important protocol deviation
LDL-C	low-density lipoprotein cholesterol
MedDRA	Medical Dictionary for Regulatory Activities
ММТТ	Mixed meal tolerance test
PD	pharmacodynamic(s)
PI	Principle investigator
РК	pharmacokinetic(s)
PR interval	PR interval is measured from the beginning of the P wave to the beginning of the QRS complex in the heart's electrical cycle as measured by ECG
QRS interval	QRS interval the interval between the Q wave and the S wave in the heart's electrical cycle as measured by ECG; represents the time it takes for the depolarization of the ventricles
QT interval	QT interval is a measure of the time between the start of the Q wave and the end of the T wave in the heart's electrical cycle as measured by ECG
QTc interval	QT interval corrected for heart rate using accepted methodology
RR	respiratory rate
SAE	serious adverse event

List of Abbreviations and Definition of Terms

Abbreviation or Term	Definition/Explanation		
SC	Subcutaneous		
TEAE	Treatment emergent adverse event		
t _{max}	time to maximum serum concentration		

1. Introduction

The purpose of this Statistical Analysis Plan (SAP) is to provide details of the statistical analyses that have been outlined within the protocol amendment 3 for study 20170139, AMG 598 dated 25 June 2019. The scope of this plan includes the primary analysis and the final analysis that are planned and will be executed by the Amgen Global Biostatistical Science department unless otherwise specified.

2. Objectives, Endpoints and Hypotheses

2.1 Objectives and Endpoints

Objectives		Endpoints			
Primary					
 To assess the safe of multiple subcuta doses of AMG 598 alone or in combina liraglutide in subject Secondary To characterize the SC doses of AMG salone or in combina liraglutide in subject 	e PK of multiple administered ation with sts with obesity PK of multiple 598 administered ation with	 Safety laboratory data, vital signs, and electrocardiograms (ECGs) AMG 598 PK parameters may include, but are 			
Exploratory					
To characterize the AMG 598	PD effects of	PD 0	c-peptide, glucose dependent insulinotropic polypeptide (GIP), glucagon-like polypeptide type 1 (GLP-1), glucagon, and free fatty acid (FFA) Concentration-time profiles and AUC for metabolic parameters following a mixed meal tolerance test (MMTT) Lipid levels, including but not limited to, total cholesterol, low density lipoprotein cholesterol (LDL-C), high density lipoprotein cholesterol (HDL-C), and triglycerides Hemoglobin A1c (HbA1c)		

Objectives	Endpoints		
• To assess the effects of AMG 598 on body weight, waist circumference and body mass index (BMI)	 Change in body weight, waist circumference, and BMI 		
 To assess the effect of AMG 598 on bone mineral density by dual energy x-ray absorptiometry (DXA) (cohorts 1-6) 	 Changes in bone mineral density as measured by DXA (cohorts 1-6) 		
To assess the effect of AMG 598 on body composition (cohort 7)	 Changes in body composition as measured by whole body DXA (cohort 7) 		
To evaluate the immunogenicity of AMG 598	Incidence of anti-AMG 598 antibody formation		

2.2 Hypotheses and/or Estimations

- AMG 598 will be safe and well tolerated following multiple SC dose administrations in subjects with obesity across the dose range evaluated
- AMG 598 in combination with liraglutide will be safe and well tolerated following multiple SC dose administrations in subjects with obesity across the dose range evaluated
- AMG 598 PK profile following multiple SC dose administrations will support selection of dose and frequency of administration in future multi-dose trials of AMG 598

3. Study Overview

3.1 Study Design

This is a randomized, placebo-controlled, double-blind, multiple ascending dose study in subjects with obesity. The study consists of a total of 7 cohorts; 3 cohorts (1, 3 and 5) with administration of AMG 598 or matching placebo SC every 4 weeks (Q4W) x3, 3 cohorts (2, 4 and 6) with Q4W x3 SC administration of AMG 598 or matching placebo in combination with liraglutide SC once daily (QD) ascending doses, and 1 cohort (cohort 7) with SC administration of AMG 598 or matching placebo SC Q4W x3 in addition to liraglutide (3.0 mg SC QD) in subjects who have been on a stable dose of liraglutide (3.0 mg SC QD) for at least 6 months. In cohorts 1-6,

eight (8) subjects will be randomized to receive AMG 598 or placebo SC in a 3:1 ratio as described in the table below. In cohort 7, sixty (60) subjects will be randomized in a 1:1 ratio to receive AMG 598 or placebo SC as described in the table below.

Cohort	# Subjects	Product	Product Dose/ Frequency Route		N (active: placebo)
1	8	AMG 598/Placebo	70 mg Q4W x 3	SC	6:2
2	8	AMG 598/Placebo	70 mg Q4W x 3	SC	6:2
		+ Liraglutide	+ 0.6, 1.2, 1.8, 2.4, 3.0 mg QDª	SC	
3	8	AMG 598/Placebo	210 mg Q4W x 3	SC	6:2
4	8	AMG 598/Placebo	210 mg Q4W x 3	SC	6:2
		+ Liraglutide	+ 0.6, 1.2, 1.8, 2.4, 3.0 mg QD ^a	SC	
5	8	AMG 598/Placebo	420 mg Q4W x 3	SC	6:2
6	8	AMG 598/Placebo 420 mg Q4W x 3		SC	6:2
		+ Liraglutide	+ 0.6, 1.2, 1.8, 2.4, 3.0 mg QDª	SC	
7	60	AMG 598/Placebo + Liraglutide	420 mg SC Q4W x 3 based on the safety, PK and PD from cohorts 1– 6 + 3.0 mg QD ^b	SC	30:30

Planned Dose Levels by Cohort

^a Subjects will start the first dose of liraglutide (0.6 mg, SC QD) on day 1, and increase the dose of liraglutide by 0.6 mg dose increment every 7 days, up to the full dosage of 3.0 mg by week 5 and remain on 3.0 mg until day 84, inclusive

^b Subjects eligible for the study will have been on a stable dose of liraglutide 3.0 mg SC QD for at least 6 months and will continue liraglutide 3.0 mg SC QD throughout the screening and study period from study days -56 to end of study (EOS) (day 207)

A dose level review meeting (DLRM) will be held to review the data and monitor safety before escalation to the next higher dose or expansion to the liraglutide combination cohort. The DLRM members will be composed of, at minimum, the investigator(s) actively enrolling subjects (whether in screening or enrolled) at the time of the meeting, the Amgen Medical Monitor, and Amgen Global Safety Officer or designee, and Amgen Study Manager or designee. Additional members may be added as needed (eg, PK/biomarker scientist, Biostatistician, or others providing expanded expertise).

The DLRM voting members include the principal investigator(s) or designee, Amgen Medical Monitor and Amgen Global Safety Officer or designee.

Escalation to a higher dose cohort or expansion to liraglutide combination cohorts will only proceed when the previous dose regimen has been found to be safe and reasonably tolerated based on available safety and laboratory data through day 36 for a

minimum of 6 of the 8 subjects dosed, and upon unanimous recommendation at the Dose Level Review Meeting (DLRM). The dose level for cohort 7 will be chosen based on the preceding cohorts' safety and PK data. The dose level for cohort 7 will not exceed the highest dose evaluated in cohorts 1-6. The planned dose escalation schedule may be modified based on treatment-emergent data (safety and/or PK). Dose adjustments (if any) will be made on a treatment cohort and not on an individual subject basis and will be agreed upon by Amgen in conjunction with the Principal Investigator. Clear stopping rules will be followed, and ad hoc DLRMs will be held, if necessary.

Enrollment can be initiated in the subsequent cohorts after the planned DLRMs. The DLRMs will take place at the following time points:

DLRM #1: After a minimum of 6 out of 8 subjects dosed in cohort 1 complete study day 36. Enrollment in cohorts 2 and 3 can be initiated after DLRM #1.

DLRM #2: After a minimum of 6 out of 8 subjects dosed in each cohort 2 and 3 complete study day 36. Enrollment in cohorts 4 and 5 can be initiated after DLRM #2.

DLRM #3: After a minimum of 6 out of 8 subjects dosed in each cohort 4 and 5 complete study day 36. Enrollment in cohort 6 can be initiated after DLRM #3.

DLRM #4: After a minimum of 6 out of 8 subjects dosed in cohort 6 complete study day 36. Enrollment in cohort 7 can be initiated after DLRM #4.

3.2 Sample Size

Approximately 108 subjects (8 per cohort, cohorts 1-6; 60 in cohort 7) will be enrolled.

The sample size for the study is based on practical considerations. For safety considerations, with up to 66 subjects receiving AMG 598 (6 subjects in each of cohorts 1-6 and 30 subjects in cohort 7), there is a 96.6% chance of detecting an adverse event with a true incidence rate of 5% or greater and a 99.9% chance of detecting an adverse event with a true incidence rate of 10%.

In cohort 7, with a sample size of 30 subjects per group, there is approximately an 80% probability of observing a mean treatment difference in percent change from baseline in body weight between AMG 598 and placebo of > 3%, assuming a true treatment difference of 5%. This assumes a standard deviation for percent change from baseline in body weight of 7% in each treatment group.

Replacement of subjects:

Subjects who withdraw from the study or who discontinue study drug administration prematurely may be replaced at the discretion of Amgen in consultation with the investigator. The replacement subject will be assigned to receive the identical treatment as the replaced subject.

3.3 Adaptive Design

Not applicable

4. Covariates and Subgroups

4.1 Planned Covariates

Baseline values may be used as a covariate in analyses.

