5.1 Overall Design

This is a randomized, placebo-controlled, double-blind, multiple ascending dose study in subjects with obesity. The study consists of 7 cohorts with SC administration of AMG 598 or matching placebo with and without liraglutide.

Approximately 108 subjects (8 per cohort for cohorts 1-6, 60 for cohort 7) will be enrolled. This study will be conducted at approximately 30 sites in the US.

For cohorts 1 to 6, eight subjects will be randomized to receive AMG 598 or placebo SC every 4 weeks (Q4W) x 3 in a 3:1 ratio at the proposed dose levels of 70, 210, and 420 mg on days 1, 29, and 57. All subjects in cohorts 1, 3, and 5 will undergo MMTT on day -1, 6 (+/- 1 day), and day 64 (+/- 1 day). Subjects in cohorts 2, 4, 6 and 7 will also receive liraglutide at up to 3.0 mg SC QD per the treatment schedule.

For cohort 7, sixty subjects that have been on a stable dose of liraglutide (3.0 mg SC QD) for at least 6 months will be randomized in a 1:1 ratio to receive AMG 598 or placebo. Subjects will continue to receive liraglutide (3.0 mg SC QD) and receive one dose of placebo on day -28, as part of a 4-week run-in. Subjects will then receive AMG 598 420 mg or placebo SC Q4W on days 1, 29, 57 in addition to stable liraglutide (3.0 mg SC QD).

Escalation to a higher dose cohort (cohorts 1 to 6) will only proceed when the previous dose regimen has been found to be safe and reasonably tolerated based on available safety and laboratory data through study day 36 for at least 6 out of 8 subjects dosed and upon unanimous recommendation at the DLRM. The planned dose escalation schedule may be modified based on treatment-emergent data (eg, safety and/or PK). Subsequent dosing will be guided by tolerability and safety. Dose adjustments for AMG 598, if any, will be made on a treatment cohort and not on an individual subject basis, and will be agreed upon by Amgen in conjunction with the Principal Investigator.

The overall study design is described by a study schema in Section 2.1. The endpoints are defined in Section 4.1.

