5.5 Patient Input on Study Design

No patient input was obtained for the study design.

6. Study Population

Investigators will be expected to maintain a screening log of all potential study candidates that includes limited information about the potential candidate (eg, date of screening).

For Cohorts 1-6, eligibility criteria will be evaluated during screening period.

For Cohort 7, eligibility criteria will be evaluated during the screening period. Subjects will not be randomized into a treatment group until after successful completion of the run-in period. Subjects who do not complete the run-in or Part 2 criteria at Day 1 will be removed from study and may be replaced.

Before any study-specific activities/procedures, the appropriate written informed consent must be obtained (see Section 12.3).

Prospective approval of protocol deviations to recruitment and enrollment criteria, also known as protocol waivers or exemptions will not be provided.

6.1 Inclusion Criteria: Part 1

Subjects are eligible to be included in the study only if all of the following criteria apply:

- 101 Subject has provided informed consent prior to initiation of any study specific activities/procedures
- 102 Males and females \geq 18 to \leq 65 years of age, at the time of signing the informed consent

- 103 Capable of giving signed informed consent which includes compliance with the requirements and restrictions listed in the consent form and in the protocol
- 104 Except for obesity, otherwise healthy (or for cohort 7, medically stable as described below) as determined by the investigator or medically qualified designee based on a medical evaluation including medical history, physical examination, laboratory tests, and ECGs on day -2 (cohorts 1, 3, and 5), or day 1 (cohorts 2, 4, and 6), and at screening (cohorts 1-7)

For cohort 7, chronic stable medical conditions that are not otherwise excluded are permitted if in the opinion of the investigator, and the Amgen Medical Monitor if consulted, do not pose a risk to subject safety or interfere with the study evaluation, procedures or completion.

- 105 Body mass index (BMI) between \geq 30.0 kg/m² and \leq 40.0 kg/m²
- 106 Have a stable body weight (less than 5 kg self-reported change during the previous 8 weeks) prior to screening

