10.1 Sample Size Determination

The sample size for the study is based on practical considerations. For safety considerations, with up to 66 subjects receiving AMG 598 (6 subjects in each of cohorts 1-6 and 30 subjects in cohort 7), there is a 96.6% chance of detecting an adverse event with a true incidence rate of 5% or greater and a 99.9% chance of detecting an adverse event with a true incidence rate of 10%.

In cohort 7, with a sample size of 30 subjects per group, there is approximately an 80% probability of observing a mean treatment difference in percent change from baseline in body weight between AMG 598 and placebo of > 3%, assuming a true treatment difference of 5%. This assumes a standard deviation for percent change from baseline in body weight of 7% in each treatment group.

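### Cohort 7 weighs subjects before and after a 4-week run-in, but the SAP never analyses the within-subject run-in change and does not clearly set the weight baseline after it

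*SAP*

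**What the plan says.** **Run-in.** Protocol 5.1 has cohort 7 subjects stay on liraglutide and "receive one dose of placebo on day -28, as part of a 4-week run-in". Table 2-3 schedules body weight at screening, day -28 and day 1 pre-dose.

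**Sizing.** SAP 3.2, "with a sample size of 30 subjects per group", claims "approximately an 80% probability of observing a mean treatment difference in percent change from baseline in body weight" above 3%, with a true difference of 5%. It adds: "This assumes a standard deviation for percent change from baseline in body weight of 7% in each treatment group". Protocol 10.1 gives the same figures. Protocol 3.1 says cohort 7 looks at preliminary weight-loss efficacy and was sized partly for that purpose.

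**Analysis.** Weight is exploratory. SAP 9.5 (efficacy) is marked not applicable, and no weight model is named. SAP 9.6.5 summarises weight at each scheduled visit by cohort and treatment. SAP 9.7.2.4 adds absolute and percent change from baseline and a graph. SAP 4.1 says: "Baseline values may be used as a covariate in analyses". SAP 9.4 lists weight as a baseline characteristic but not run-in change.

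**Eligibility.** Criterion 106 (Protocol 6.1) asks for stable weight before screening, meaning "less than 5 kg self-reported change during the previous 8 weeks". The day 1 criteria in Protocol 6.3 and 6.4 contain no weight measure.

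**The concern.** The run-in gives a measured, pre-treatment weight trajectory on stable liraglutide. Subjects who are still losing or regaining weight add variance to percent weight change, and a chance difference in drift between two arms of 30 passes into the contrast that helped to size cohort 7. The data that could remove part of this noise are collected, but no analysis is planned for them. Because covariate use is optional, the choice could also be made after the data are seen.

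A second issue comes first in order. Run-in change can serve as a covariate only if baseline sits at the end of the run-in. If baseline sits before it, run-in drift becomes part of the reported outcome.

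**Working it through.** **Inputs.** From SAP 3.2: 30 per arm, SD 7 percentage points, true difference 5, threshold 3. Assumed, because the documents give no value: the within-arm correlation r between run-in percent change and later percent change. The main range is 0.3 to 0.5, with 0 to 0.7 shown.

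**1. The plan's own figure.**
- SE of the difference = 7 × √(2/30) = 1.807 points.
- P(observed difference > 3) = Φ((5 − 3)/1.807) = Φ(1.107) = 86.6%.

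The stated figure of about 80% is not reproduced. Two-sided 5% test power for a difference of 5 is Φ(5/1.807 − 1.96) = Φ(0.806) = 79.0%. That is close to 80%, but it is a different quantity and no test is planned. The starting point below is 86.6%.

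**2. Effect of adjusting for run-in change.** Adjusted SE = 1.807 × √(1 − r²). Equivalent unadjusted size per arm = 30/(1 − r²). The small loss from estimating the slope is ignored.

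| r (assumed) | SE, points | P(observed > 3%) | Equivalent n per arm |
|---|---|---|---|
| 0 | 1.807 | 86.6% | 30.0 |
| 0.1 | 1.798 | 86.7% | 30.3 |
| 0.3 | 1.724 | 87.7% | 33.0 |
| 0.5 | 1.565 | 89.9% | 40.0 |
| 0.7 | 1.291 | 93.9% | 58.8 |

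Over the main range the probability gains 1.1 to 3.3 points (87.7 − 86.6 and 89.9 − 86.6). The component of the SE that adjustment removes is r × 1.807, which is 0.54 to 0.90 points.

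**3. Where baseline falls.**
- SAP 5 takes the last assessment before the first dose of investigational product, and defines that product as AMG 598 or placebo. Cohort 7 receives its first placebo on day -28. Read literally, baseline weight is then the screening or day -28 value.
- SAP 5 also schedules cohort 7 randomisation, as the enrolment date, at day -28. Protocol 7.2 places it on day 1.
- Protocol 9.1.2 defines day 1 for cohort 7 as the first dose after randomisation. This points to a day 1 pre-dose baseline and is the likely intent.

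On the literal reading, the reported change is approximately the run-in change plus the on-treatment change. On the likely reading, it is the on-treatment change alone.

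**The case against.** The strongest reply is that weight is exploratory in a descriptive Phase 1b plan. Protocol 10.3.2.4.2 has exploratory analyses done only when judged appropriate. There is no weight model to add a term to, so this is a request for a new adjusted analysis. The gain rests on a correlation that nobody has supplied. SAP 9.6.5 would already tabulate day -28 and day 1 weight by arm. All of this stands, and it limits the point to precision. However, separate visit means are not a within-subject change and adjust for nothing.

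A reader might infer three stronger things that the documents do not support.

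- **That permitted drift could mimic the assumed effect.** Five kilograms is 5.0% at 100 kg and 4.2% at 120 kg, so the match with 5% is not general. It is also a per-subject limit before screening, set against a difference in arm means. If drift were uniform within ±5% (SD 5/√3 = 2.89%), chance imbalance between arms would have SE 2.89 × √(2/30) = 0.75 points. The probability of an imbalance beyond 3 points would be about 0.006%.
- **That the contrast is biased.** Randomisation with concurrent placebo balances drift in expectation. The planning SD of 7% may already include it.
- **That self-reported stability is the only safeguard.** Criteria 107 (willingness to maintain diet and activity), 111 (at least 6 months on liraglutide 3.0 mg), 113 (liraglutide compliance) and 222 (weight-active drugs and extreme diets), with Protocol 7.1.7 during the study, also limit drift.

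**Conclusion.** The point holds as a missed precision gain and an unclear baseline. The SAP leaves the measured run-in change unanalysed, and its literal baseline could include that change in the outcome. At an assumed r of 0.3 to 0.5, adjustment is worth about 3 to 10 extra subjects per arm (33.0 − 30 and 40.0 − 30). At r near 0.1 it is worth almost nothing. The correlation may be low: persistent drift pushes it up, while measurement error in the shared day 1 weight pushes it down. No primary or secondary endpoint, planned test or eligibility decision is affected. The change is worth making because it is cheap and because it settles the baseline and the covariates in advance.

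**What to change.** 1. In SAP 5 and 9.7.2.4, define the cohort 7 weight baseline as the day 1 pre-dose value. In the same edit, reconcile the cohort 7 enrolment-date entry in SAP 5 with Protocol 7.2.
2. In SAP 4.1 and 9.7.2.4, pre-specify a supportive ANCOVA of percent weight change at a named visit. Its terms are treatment, day 1 weight, and run-in percent change from day -28 to day 1. Report it beside the unadjusted summary.
3. In SAP 9.4, tabulate run-in percent weight change by arm for cohort 7.

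The cost is one added supportive model, one extra degree of freedom for the run-in term, and one table row. The gain will be small if the correlation is low. No new visit, measurement or eligibility rule is needed.
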